Randomization (1:1) will be done through central allocation of a block-randomization schedule prepared through a computer-generated random listing. Randomization will be done by the study data analyst at the Hospital for Sick Children. The analyst will be the only member of the investigative team aware of the randomization assignment and will not be directly doing the statistical analysis. He/she will not be involved in the care of the study patients or the measurement of outcomes in the study. No other research staff nor patients nor physicians will be aware of the randomization assignment. The pharmacist at each study site will call the analyst for randomization.

Once the patient is randomized, the analyst will inform the research pharmacy at each study site and they will distribute either prednisone or placebo (lactose, packaged in #0 capsules of identical appearance) to the hospital ward or the CF clinic according to dosing Table 1. Physicians and patients will be blinded to the treatment, and placebo will be produced to look identical to the treatment drug. The microbiology lab and pulmonary function lab will also be blinded to the treatment allocation. Compliance will be measured by nurses for hospitalized patients and by asking patients to return any unused medication for patients receiving homecare IV antibiotics.

Safety monitoring

Patients who are most at risk of developing side effects secondary to corticosteroid use will be excluded based on the above exclusion criteria. Subjects will be monitored with measurements of urine glucose on day 7, day 10 (\pm 2 days) and on day 14 of antibiotic treatment while on prednisone (or placebo). If the urine glucose is $> 2+$, a serum glucose measurement will be performed. All the information will be provided to the treating physicians; they can decide at any time to withdraw their patient and request unblinding of the treatment allocation. The study will be monitored by a Data Safety Monitoring Board (DSMB) (Appendix 1.2-Data Safety Monitoring Plan).

E. Study outcomes:

Primary outcome:

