pulmonary function data points were available (n=228), we determined that 50% of patients will recover >90% of their baseline FEV₁ at day 7 of antibiotic treatment, with the remaining 50% available for randomization to either prednisone or placebo treatment. Of the 50% who do not recover >90% of baseline FEV₁ at day 7, 30% of these will go on to recover FEV₁ at day 14 of antibiotic treatment. We therefore estimated a 30% placebo response rate. Using these estimates, we calculated the sample size (**power two proportions** command in Stata 13.1) for the comparison of two proportions (Table 3).

For this study, we are aiming for a clinically significant treatment effect size of approximately two and a half-fold (30% response in the placebo arm vs 60% in the treatment arm). In order to have 80% power (at a significance level of 5%) we would need a sample size of **84 (42/arm)**. Estimating a 50% participation rate and a 20% drop out rate, we will need to approach 210 patients.

Since 50% of all patients who present with a PEx recover their lung function by day 7 of antibiotic therapy, 30% of patients will not experience more than a 10% relative drop in FEV₁ (inclusion criteria) and 10% of CF patients have diabetes and are on insulin which is an exclusion criteria (CPDR 2012 and personal communication-CF clinic directors), we will need to screen approximately 650 exacerbation events to approach 210 patients and enroll 105 patients into the study (Table 3). Over the 3 year study period, we expect to enroll enough study participants from all study sites) which will give us a sufficient population from which to enroll our necessary study sample size. We have had face to face meetings and discussions with our team of co-investigators who have been involved in the design and are fully committed to participating in this study. We have successfully collaborated with this team of researchers in previous clinical trials (10, 51) and fully expect we will achieve our current stated aims.

G. Statistical analyses

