When target sample size is reached, the study statistician (who will not be involved in the conduct of the study) will unblind the treatment allocation (identify who is in group A vs B but not identify the groups themselves as active drug or placebo) and estimate the treatment effect between the two groups based on the primary outcome (intention-to-treat). If there is a statistically significant treatment effect ($p<0.05$), the study statistician will do the following statistical analyses. For the primary outcome we will compare the proportion of randomized patients that responded at day 14 of therapy in the placebo arm compared with the treatment arm using a two sample test for proportions. We will perform intent-to-treat analysis according to the treatment arm subjects were randomized to. We will also perform a per-protocol analysis based on subjects who completed the 7 days of prednisone or placebo as per protocol. The same analysis will be performed for the proportion responding to therapy at 1 month. Logistic regression analysis will then be performed to adjust for potential confounders, such as age, gender, *Pseudomonas aeruginosa* or methicillin-resistant *Staphylococcus aureus* (MRSA) infection and lower FEV₁, as these factors have been associated with failure to recover lung function after an exacerbation (3, 25). For the additional secondary outcomes, absolute change in pulmonary function tests, length of hospitalizations and change in sputum measurements,

we will use parametric (t-test), or non-parametric (Mann-Whitney) two sample comparison test. Linear regression analysis will be then performed to adjust for potential confounders, as listed above. Time to subsequent exacerbation will be compared using a Cox proportional hazard model. Potential confounders will be adjusted for in the Cox-proportional hazard model. All secondary outcomes will be analyzed both as intention-to-treat and per-protocol. All outcomes will be obtained for all subjects irrespective of whether they completed the study per protocol. In the case of missing data, we will perform the analysis on complete (complete case analysis). To determine whether diabetic patients have a different response compared to non-diabetic patients, we will perform a sensitivity analysis comparing return to baseline lung function in diabetics vs non-diabetics according to treatment group.

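### The diabetes analysis contrasts diabetic with non-diabetic patients by arm, so as written it does not estimate whether the prednisone effect differs by diabetes status

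*Combined protocol and SAP*

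**What the plan says.** Section G gives the purpose, "To determine whether diabetic patients have a different response compared to non-diabetic patients", and then the method: "we will perform a sensitivity analysis comparing return to baseline lung function in diabetics vs non-diabetics according to treatment group". It names no test, effect scale, confidence interval or interpretation rule for this analysis. No treatment-by-diabetes interaction appears anywhere in the document. As Section G is written, the listed analyses follow only if the primary comparison reaches p<0.05.

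Diabetes is not among the examples of adjustment variables in Section G. The allocation text, "Randomization (1:1) will be done through central allocation of a block-randomization schedule", names no stratification factor.

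The document does not say how many diabetics to expect, and three places conflict on insulin-treated patients:
- Section F (Sample size calculation) deducts them from the pool: "10% of CF patients have diabetes and are on insulin which is an exclusion criteria".
- The exclusion list in Section C does not contain insulin-treated diabetes.
- The Safety Monitoring Plan in Appendix 1.2 sets out glucose monitoring for insulin-treated participants.

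**The concern.** The purpose is a question about effect modification: does adding prednisone change the chance of recovery by a different amount in diabetics? That is a difference between two randomised prednisone-placebo contrasts. The stated method compares diabetics with non-diabetics by arm. If diabetics recover less often whatever they receive, that comparison shows a gap even when prednisone works equally well in both groups.

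The label does not fit either. A sensitivity analysis asks whether the primary result is robust, whereas this sentence asks a subgroup question.

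The answer will be read. Appendix 1.2 reports glucosuria in 6 prednisone and 1 placebo subjects in the earlier pilot trial, and it expects that glucose control may be disrupted in insulin-treated participants. A statement that prednisone does or does not help diabetics would carry weight with clinicians, so it should rest on the randomised contrast.

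**Working it through.** **Inputs.** From Section F: "30% response in the placebo arm vs 60% in the treatment arm", 84 patients (42 per arm), 5% significance, 80% power. Two-sided testing is not stated. It is assumed here, and it reproduces the plan's figure. The number of diabetics is not given; 4, 8 or 13 per arm (about 10%, 20% or 30%) is an assumed range.

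**The plan's own figure.** n per arm = [1.96·√(2·0.45·0.55) + 0.8416·√(0.30·0.70 + 0.60·0.40)]² / 0.30² = (1.379 + 0.565)² / 0.09 = 41.97, so 42 per arm, as stated.

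**Check 1: diabetics versus non-diabetics tested within each arm.** The true response is 30% on placebo and 60% on prednisone in both groups, so diabetes changes nothing. The probability that one arm is significant and the other is not is a(1−b) + b(1−a), where a and b are the chances of significance in the two arms.

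| Diabetics per arm | z test | Fisher test |
|---|---|---|
| 4 | 7.7% | 4.0% |
| 8 | 8.9% | 6.3% |
| 13 | 9.9% | 7.2% |

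Now let diabetes be prognostic while the treatment odds ratio stays at 3.5 in both groups. The prognostic odds ratios are assumptions. At 0.5, diabetics respond in 17.6% (placebo) and 42.9% (prednisone), and disagreement is 12-25% (z test). At 0.33 it is 20-42%. Equal odds ratios do not mean equal risk differences, so the other scale was checked too. With a risk difference of 0.30 in both groups (diabetics 15% versus 45%), disagreement is about 19% at 8 per arm and 26% at 13 per arm (z test).

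The comparison also misses real differences. If prednisone does nothing in diabetics (30% in both arms), the prednisone-arm comparison is significant in only 23-43% of trials (z test).

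**Check 2: prednisone versus placebo tested separately in diabetics and in non-diabetics.** The true response is again 30% versus 60% in both groups.

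| Diabetics per arm | Test | Power, diabetics | Power, non-diabetics | Groups disagree |
|---|---|---|---|---|
| 4 | z | 17.1% | 76.1% | 67.2% |
| 4 | Fisher | 3.1% | 68.2% | 67.1% |
| 8 | z | 28.9% | 70.4% | 58.6% |
| 8 | Fisher | 13.3% | 62.2% | 59.0% |
| 13 | z | 41.0% | 63.6% | 52.4% |
| 13 | Fisher | 25.9% | 53.0% | 51.5% |

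In simulation, disagreement was 59-78% among trials with a significant primary result, which are the trials in which Section G runs these analyses.

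**Check 3: what an interaction contrast can deliver.** Take the risk difference in diabetics minus that in non-diabetics, with d diabetics per arm. Since 0.30·0.70 + 0.60·0.40 = 0.45, SE = √(0.45/d + 0.45/(42−d)).
- d = 4: √(0.1125 + 0.0118) = 0.353; half-width 1.96·0.353 = 0.69
- d = 8: √(0.0563 + 0.0132) = 0.264; half-width 0.52
- d = 13: √(0.0346 + 0.0155) = 0.224; half-width 0.44

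If prednisone does nothing in diabetics and has its full effect in the rest, power to detect that is about 14%, 21% and 28% respectively.

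**Check 4: sparse cells.** With 4 diabetics per arm, the chance that at least one arm has all or no responders among its diabetics is 1 − (1 − 0.3⁴ − 0.7⁴)(1 − 0.6⁴ − 0.4⁴) = 1 − 0.752·0.845 = 36%. An ordinary logistic interaction then has no finite estimate. At 8 and 13 per arm the chance is about 7% and 1%.

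**The case against.** The strongest reply is that this is one short sentence about a secondary analysis. Recovery tabulated by diabetes status and by arm gives the four cells from which both treatment differences, and the gap between them, follow directly. The wording does not forbid that step, and no significance rule or subgroup claim is written down. This is fair as far as it goes: a careful statistician might compute the right contrast. But the plan does not name it, and the comparison it does name is a different one.

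A reader might infer that the planned analysis will more likely than not give a false signal. The documents do not support that. Rates above one half arise only in Check 2, where prednisone and placebo are tested separately in each group and the p-values compared. The text leaves room for that reading but does not state it. For the comparison it does describe, the false-signal rate is 4-10% without a prognostic effect and about 42% at the strongest prognostic effect assumed.

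A reader might also take 10% as the trial's share of diabetics, giving about 8 of 84. Section F gives that figure for insulin-treated CF patients whom it calls excluded. It is neither all diabetics nor a forecast of those randomised.

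Finally, an interaction analysis would rarely settle the question at this sample size. That stands. It supports reporting an estimate with its interval, and does not justify keeping a contrast that targets something else.

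**Conclusion.** The point holds in limited form. The stated comparison is between non-randomised groups and does not estimate whether the prednisone-placebo effect differs by diabetes status. It can mislead in two ways: if diabetes is prognostic (12-42% disagreement between arms by z test at equal odds ratios, under assumed prognostic odds ratios of 0.5 to 0.33), or if separate within-group p-values are compared (about 51-67% disagreement with identical effects). All these figures rest on 42 per arm, the plan's 30% and 60% response rates and an assumed 4 to 13 diabetics per arm. The true number cannot be derived while the exclusion list, Section F and Appendix 1.2 disagree on insulin-treated patients. This is a minor point, because the primary comparison does not depend on it.

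**What to change.** Replace the sentence in Section G with a pre-specified exploratory subgroup analysis in the randomised patients:
- Drop the sensitivity-analysis label and define diabetes status from information available before randomisation.
- Report the prednisone-placebo risk difference with 95% confidence interval in diabetics and in non-diabetics.
- Report the treatment-by-diabetes interaction with its 95% confidence interval, as the difference in risk differences, as a penalised or exact logistic interaction, or as both. State the scale in advance, since equal effects on one scale need not be equal on the other. Do not rely on ordinary logistic regression, given the sparse cells.
- State that no subgroup conclusion will be drawn from separate p-values.
- Reconcile the exclusion list in Section C, Section F and Appendix 1.2 on insulin-treated diabetics, and give the expected number of diabetics as unknown until then.

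The cost is analysis-plan wording. No new data are needed, since the planned analysis already requires diabetes status. The downside is an interaction estimate with a half-width of about 0.44 to 0.69 on the risk-difference scale, which the report should say plainly.

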Patients will be randomized to receive either oral prednisone 2 mg/kg/day (max 60 mg; rounded to the nearest 10 mg) (Table 1) divided twice daily or oral placebo twice daily for 7 days in addition to the IV antibiotics prescribed by their physician (**Randomization**). On Day 7 only, it may be necessary on some occasions when the study drug (prednisone or placebo) is not available until the late afternoon, to give the study drug as one full dose (as opposed to twice daily). The choice and duration of antibiotic therapy will be left completely to the discretion of their treating physician. Study outcome measures will be obtained for all enrolled subjects at day 0 (± 2 days) and subsequently at day 7 (± 2 days), day 14 (± 2 days) of IV antibiotic treatment and at the 1 month follow up visit (approximately 1 month after day 14), as per usual standard of care (; **Table 2 Study Design Schedule**). However, day 0 may + 3 days when impacted by a Friday or long weekend admission/IV antibiotic start time. Patients who are receiving home IV antibiotic therapy for a PEx will also be eligible as they return to clinic weekly according to standard clinical care.

During the course of their admission, for patients willing to provide samples, the following specimens will be collected for the bio-repository for future analysis. All biological samples will be labeled using the patient's study number. The patient's study number will be linked to patient identifiers only by a master list that is managed by the PI and the Research Coordinator of this study:

- Sputum for inflammatory markers— For patients who can produce sputum, we will collect a research sputum sample which will be immediately sent on ice to collaborator [name] laboratory for processing for inflammatory markers and stored for future examination of biomarkers according to the standardized protocols developed by the Therapeutic Drug Network, US CF Foundation.

- Serum for biomarkers—Blood collection for future studies will occur at the time of clinical bloodwork or if a patient chooses to provide research blood separately. A total of 8 mls of blood will be drawn in two lavender top EDTA tubes in the phlebotomy clinic, stored on site and subsequently delivered to [name] laboratory at St. Paul's Hospital (a sub-site for the study) for final processing and storage.

Randomization and distribution of drug/placebo

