The questionnaire that will be used is the Cystic Fibrosis Questionnaire-Revised (CFQ-R) Respiratory domain (44). The CFQ-R is a disease-specific instrument that measures health-related quality of life for adolescents and adults with CF with a developmentally appropriate version for children. The CFQ-R is a reliable and valid measure of quality of life for individuals with CF and is frequently used in clinical trials to assess the effects of new therapies (45). In addition, subjects will also be asked to complete the CF Respiratory Symptom Diary (CFRSD) on day 0, day 7, day 14 and at the 1 month follow up visit(46). The Chronic Respiratory Infection Symptom Score will be applied to the CFRSD to calculate a severity score from 0-100 (100 being most severe). The CRISS score has been previously shown to be a responsive measure of steroid treatment effect in CF pulmonary exacerbations(47).

iv)The length of hospitalization and duration of IV antibiotic treatment in each treatment arm.

Length of hospitalization (number of days in hospital) and duration of IV antibiotic treatment are clinically relevant and patient-meaningful outcomes that will be calculated for each patient and compared between treatment groups.

v) The time to subsequent PEx in each treatment arm.

Based on our previous study, we know that the time between exacerbations is one of the most important determinants of overall lung function decline in an individual with CF (6). Time to subsequent pulmonary exacerbation will be calculated from the last day of IV antibiotic therapy of the randomized exacerbation to the first day of re-starting IV antibiotic treatment for a new pulmonary exacerbation (minimum 21 days between events). We will compare the average (or median if data not normally distributed) duration between treatment groups. We will follow up patients for subsequent exacerbations for 1 year following their randomized exacerbation.

vi) The number of adverse events and withdrawals from study recorded in each treatment arm.

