If when the statistician estimates the treatment effect between the two groups (above), there is NOT a statistically significant treatment effect ($p>0.05$), the statistician will re-calculate the sample size based on the observed data from 84 participants, in order to determine what sample size is required to observe a statistically significant effect. This data will be provided to the DSMB who will decide whether or not to continue the study, based on feasibility and the clinical relevance of the treatment effect size. Appendix 1.1 includes detailed plans for the analysis of the extension study, which will be designed as an adaptive trial (52).

H. Potential Challenges and Alternative Approaches

The main challenge of this study is the large estimated treatment effect size. The future adaptive trial design, however, allows us the flexibility to calculate the necessary sample size based on observed data if the difference between groups is clinically but not statistically significant. These data will inform the decision whether to continue the trial with the addition of other centers in either Canada or the United States (Deliverables and Future Directions). Another challenge is the number of potential confounders influencing lung function recovery. We have designed this trial to be pragmatic, that is, reflective of real life conditions, as it is not possible to stratify based on all the variables that could affect response such as concomitant medications, hospital vs home IV therapy, choice and duration of antibiotic therapy. Therefore, we will collect all this information and sensitivity analyses will be done to determine whether these variables affect the results.

I. Personnel Requirements and Study Timeline:

We will require a research coordinator at each site over the study period (see Budget).

J. Knowledge Translation (KT):

We have developed a KT plan with the assistance of [name], scientific director of KT at the Hospital for Sick Children (Appendix). Our target audiences for the results of this study are CF clinicians, patients and researchers. We will partner with CF Canada to implement the following KT strategies for disseminating our results: publishing in an open-access journal for all audiences, presenting at national (Canadian Clinics conference) and international CF

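### Total IV antibiotic duration is listed as a confounder for sensitivity analysis, although it is completed after randomisation and is itself a secondary outcome

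*Combined protocol and SAP*

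**What the plan says.** Section H (Potential Challenges and Alternative Approaches) raises the issue this way: "Another challenge is the number of potential confounders influencing lung function recovery". It says the trial cannot stratify on everything and, after giving concomitant medications as one example, continues: "hospital vs home IV therapy, choice and duration of antibiotic therapy. Therefore, we will collect all this information and sensitivity analyses will be done". The commitment in full is that "sensitivity analyses will be done to determine whether these variables affect the results". It states neither a method nor a time point for each variable.

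Three other places bear on duration:

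- Section D (Study protocol) places randomisation after the day-7 (± 2 days) lung function test, for patients who have not recovered more than 90% of baseline FEV1.
- Section D also says: "The choice and duration of antibiotic therapy will be left completely to the discretion of their treating physician".
- Section E lists as secondary outcome iv "The length of hospitalization and duration of IV antibiotic treatment in each treatment arm", and describes these measures as "clinically relevant and patient-meaningful outcomes that will be calculated for each patient and compared between treatment groups".

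Section G sets the primary analysis as an unadjusted intention-to-treat comparison of two proportions at day 14. It adds a logistic model whose named covariates are age, gender, *P. aeruginosa* or MRSA infection and lower FEV1. Antibiotic duration is not named there, although the list is given only as examples.

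**The concern.** A confounder of a randomised comparison would have to precede randomisation and differ between the arms by chance. Total IV duration cannot play that part, because it is known only when IV therapy stops. A physician free to decide when to stop may respond to lung function recovery, which prednisone is meant to change. Duration may therefore be a consequence of both the treatment and the day-14 result. The protocol implicitly accepts this by comparing duration between arms as an outcome.

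An analysis that holds duration fixed compares prednisone and placebo patients who needed the same length of IV therapy. If better recovery shortens therapy, part of the benefit is removed by construction. The likely misreading is that a prednisone effect is not robust, or is explained by antibiotic practice, when the analysis itself produced the attenuation.

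**Working it through.** **1. The plan's own figure.** Inputs from section F: 30% versus 60% response, 80% power, 5% significance (taken as two-sided), 1:1 allocation. The pooled proportion is 0.45.

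n per arm = [1.96·√(2·0.45·0.55) + 0.8416·√(0.30·0.70 + 0.60·0.40)]² / 0.30² = (1.379 + 0.565)² / 0.09 ≈ 42.

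This reproduces 42 per arm (84 in total). Duration does not enter the calculation, so the point leaves it unchanged. The planned odds ratio is (0.60/0.40)/(0.30/0.70) = 3.50 and the planned risk difference is 0.30.

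**2. Which listed variables are affected.**

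| Section H variable | Can be fixed by day 7? | Named outcome in section E? |
|---|---|---|
| Total IV antibiotic duration | No | Yes (outcome iv) |
| Hospital or home setting | Yes, though it may change later | No (length of stay is a related outcome) |
| Antibiotic choice | Yes, though it may change later | No |
| Concomitant medications | Yes, though they may change later | No |

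Only duration is both on the list and an outcome.

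**3. Continuous FEV1 (part of secondary outcome ii).** Let FEV1 be F = dT + e, where T is arm, and let duration be D = −bF + u, so that therapy is shorter when recovery is better. With ρ the within-arm correlation of D and F, the coefficient on T adjusted for D is d(1 − ρ²).

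- ρ = 0.3: 1 − 0.09 = 0.91, a 9% loss
- ρ = 0.5: 1 − 0.25 = 0.75, a 25% loss
- ρ = 0.6: 1 − 0.36 = 0.64, a 36% loss

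Simulation with 400,000 patients gives the same fractions.

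**4. Binary primary outcome, same structure.** Response is F above a cut-off that gives 30% and 60%. A logistic model of response on arm and duration, with the risk difference standardised over the sample, gives:

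| Assumed ρ | Odds ratio | Risk difference |
|---|---|---|
| 0 | 3.53 | 0.30 |
| 0.3 | 3.37 | 0.27 |
| 0.5 | 3.08 | 0.23 |
| 0.6 | 2.87 | 0.19 |

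The 3.53 differs from 3.50 only by simulation error. On the log odds scale the losses are about 4%, 11% and 16%, for example 1 − ln(2.87)/ln(3.53) = 1 − 1.054/1.261 = 16%. In simulated trials of 42 per arm, the adjusted arm effect is significant in about 81%, 75%, 61% and 55% of trials at ρ = 0, 0.3, 0.5 and 0.6, give or take two or three points.

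**5. Sensitivity to the assumed structure.** Suppose instead that duration depends only on responder status. Assume a mean of 17 days in placebo non-responders and an SD of 4 days, with responders stopping 3 days earlier. The adjusted odds ratio is then 3.49, essentially unchanged, because P(Y | T, D) is proportional to P(Y | T)·P(D | Y). The risk difference still falls, to 0.27. If prednisone also shortens duration by 1 day at equal response, the odds ratio is 2.92 and the risk difference 0.23. Restricting to patients with at least 14 days of therapy gives risk differences of 0.28 and 0.25 in these two cases, so restriction does not avoid the problem. If duration does not depend on response, neither measure moves.

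**The case against.** The strongest reply is that this is one word in an exploratory sentence. Section H does not say that any model will adjust for duration, and the adjusted models in section G do not name it. The only other sensitivity analysis in section G compares diabetics with non-diabetics by treatment group, which is a subgroup look. The primary test is unadjusted, and its significance level and power do not depend on this sentence.

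Most of that stands, and it sets the severity. It does not remove the point: adjustment, stratification and restriction all condition on total duration, so leaving the method open does not make the analysis safe.

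A reader might also infer that every variable on the list is a post-randomisation outcome. The documents do not support that. IV therapy starts at day 0, patients on home IV therapy are eligible, and setting, antibiotic choice and concomitant medications can all be known before randomisation. Their day-7 values are legitimate covariates. For them the gap is only that section H does not say which time point will be used.

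Nor can the 9% to 36% be carried over to the primary outcome. Those figures belong to a linear model of FEV1. Under the same assumptions the log odds ratio for response loses about 4% to 16%.

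**Conclusion.** The point holds for total IV antibiotic duration and is minor. The plan treats one variable both as an outcome and as a confounder, and an analysis conditioned on it can understate a real effect.

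The size is illustrative, because the documents give neither a distribution of duration nor its correlation with FEV1. At assumed correlations of 0.3 to 0.6, the continuous effect shrinks by 9% to 36%, the odds ratio for the primary outcome falls from about 3.5 to between 3.4 and 2.9, and the risk difference falls from 0.30 to between 0.27 and 0.19. At zero correlation there is no bias. If duration tracks only responder status, the odds ratio is preserved while the risk difference still falls. Attenuation is thus the likely direction if recovery shortens therapy, but it is not certain.

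It would be wrong to conclude that the trial's main result is biased. The primary intention-to-treat comparison and the 42 per arm are untouched.

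**What to change.** In section H, remove total IV antibiotic duration from the variables for sensitivity analysis and state that it will be analysed, with length of hospitalisation, only as an outcome by arm. For care setting, antibiotic choice and concomitant medications, specify the value at or before randomisation (day 7), and say whether each will be used as a covariate or as a subgroup. If the sponsor wants to study changes after day 7, that needs its own stated estimand and method. The wording should be settled before the treatment groups are unblinded.

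The text change is one or two sentences and alters no treatment, visit or sample size. It has two costs. First, section H promises to collect this information but gives no time point, and Table 2 shows no day-7 entry for these variables, so it should not be assumed that the values are already available. The case report form must date each one. Second, the trial gives up a simple look at whether duration explains the result, though that look could not have answered the question reliably.
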